Design: Pilot of novel care model for low-barrier care and adherence support for uptake and sustained use of biomedical HIV prevention and medications for opioid use disorder for women who inject drugs

Study Population: 50 female-identifying people ≥18 years of age and older who have ever injected drugs and are not known to be HIV-positive

Study Site: Community-based clinic on north Aurora Avenue in Seattle, WA

Primary Study Objectives:

1. Evaluate uptake of PrEP and MOUD
2. Evaluate sustained use of PrEP and MOUD
3. Evaluate treatment completion rate and time to completion after POC STI testing
4. Assess acceptability of pilot community-based care model
5. Assess acceptability of POC STI testing at community-based site.

Approach: We will conduct a pilot study of a community-based novel care model developed with community feedback and a community advisory board (CAB) co-design process during phase I of this project. We will enroll 50 female-identifying people and follow them for 6 months. We will assess uptake of PrEP and buprenorphine; POC STI testing and treatment completion rates; sustained use of PrEP and buprenorphine at months 3 and 6 (n=50). We will conduct surveys, guided by CFIR, to assess and characterize the acceptability and feasibility of venue-based primary and HIV prevention care among women who inject drugs (WWID).

Background and rationale

Women who inject drugs (WWID) experience frequent barriers to receiving primary care, especially sexual health and addiction services, because of perceived stigma, competing needs, and structural inequities within the healthcare system. Barriers to care among WWID are often exacerbated by the additional social chaos of unstable housing and engagement in transactional sex. These structural realities promote exclusion from traditional primary care systems, increase risk of HIV acquisition, and have led to rising rates of syphilis infections and overdose deaths among WWID in recent years. PrEP, buprenorphine, and STI control are key components of the End the HIV Epidemic prevention pillar and proven tools for reducing risk of HIV acquisition and opioid overdose, but uptake and sustained use of these interventions are low among WWID.

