In 2018, our team at the University of Washington established a weekly clinic, the Safe. Healthy. Empowered. (SHE) Clinic, to provide care for WWID and exchange sex. SHE Clinic is co-located and operated in collaboration with Aurora Commons, a not-for-profit drop-in center that provides basic needs and day-shelter for unhoused individuals in Seattle. HIV prevalence is approximately 10% among SHE Clinic patients, with 80% of patients engaging in injection drug use and 69% reporting exchange sex; although internal, unpublished estimates suggest the prevalence of exchange sex may be >90% in the SHE Clinic population. Initially operating only four hours per week, SHE Clinic, under the direction of [name] (co-I), has provided care to over 190 socially and medically marginalized women in Seattle. Nonemergent emergency department visits among SHE Clinic patients significant declined over a six-month period when compared with similar visits among WWID in north Seattle who had never received care at SHE Clinic. Uptake of PrEP (33%) and buprenorphine (49%) among SHE Clinic patients has improved significantly. Significant barriers to care remain for these socially and medically marginalized women. Despite the availability of PrEP and the high prevalence of HIV and HIV-risk factors in this population, sustained use of PrEP is exceedingly low (0-5%) among SHE Clinic patients after six months, as is sustained use of buprenorphine (12%) (**Preliminary Results**).

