In addition to reimbursement for each study visit, participants will receive a financial incentive of \$15 for returning to receive any test results that required off-site lab testing, as is standard of practice at our community partner, Aurora Commons/SHE Clinic. Financial incentives will be paired with low-barrier, walk-in care and adherence counseling at each visit.

Hair samples and DBS samples will be placed in individual, labeled small plastic bags and returned to study facilities at Harborview Medical Center for safe, secure storage following each clinic session.

Follow-up study visit data collection

An electronic follow-up health questionnaire will be filled out by participants in REDCap using a clinic tablet. This will occur at both the 3 and the 6-month follow-up visits. Research staff will be allowed to assist the participant in filling out the electronic health questionnaire, if the participant chooses. The questionnaire will assess sexual practices and substance use behaviors in the prior 3 months, as well as self-reported adherence to PrEP (if prescribed), barriers and facilitators to taking PrEP (if prescribed), self-reported adherence to buprenorphine (if prescribed), and barriers and facilitators to taking buprenorphine (if prescribed). At the end of the study visit, a short survey will be complete to assess the patient’s overall experience receiving care at the venue-based clinic and assess acceptability and the level of perceived stigma associated with venue-based care.

During or immediately following the visit, the clinic staff will fill out a visit summary report in REDCap, indicating the results of POC STI / HIV testing, if the participant was prescribed PrEP, reason they were not prescribed PrEP (if applicable), if the participant was prescribed buprenorphine, and reason the participant was not prescribed buprenorphine (if applicable).

Refill visits

Due to prescribing laws, participants who initiate buprenorphine-naloxone or buprenorphine will be given a maximum of one month of therapy at a time. As such, they will be asked to come

back for brief refill visits every month. No additional research data collection will occur during these refill visits. Participants will receive a \$15 incentive for returning for buprenorphine refills.

Standard of Care

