 - b. Participants who accept prescriptions for MOUD at multiple points throughout the study will only be counted once when calculating uptake.
 - c. Final analysis will present uptake as a percentage (proportion).
3. Evaluate sustained use of PrEP
 - a. PrEP: Dried blood spot (DBS) samples were obtained at each visit to assess PrEP adherence via tenofovir-diphosphate (TFV-DP) concentrations. Sustained use was defined as >4 doses/week, resulting in a DBS TFV-DP concentration of >700 fmol/sample at 3 and/or 6 months post-enrollment among those prescribed PrEP at a preceding study visit.
 - b. Final analysis will present sustained use for both PrEP as a percentage (proportion).
4. Evaluate sustained use of MOUD
 - a. MOUD: DBS samples were obtained at each visit to assess MOUD adherence via buprenorphine and norbuprenorphine concentrations, both measured in ng/mL. Sustained use was defined as any buprenorphine and/or norbuprenorphine detected, resulting in a DBS >0 ng/mL concentration of buprenorphine and/or norbuprenorphine at 3 and/or 6 months post-enrollment among those prescribed MOUD at a preceding study visit.
 - b. Final analysis will present sustained use for MOUD as a percentage (proportion).
5. Evaluate STI treatment completion rate and time to completion after POC STI testing
 - a. Treatment completion will be defined as documented treatment following a reactive POC STI test (chlamydia, gonorrhea, syphilis, and/or trichomonas). Treatment will either be indicated in the Visit Clinical Summary from the study visit or noted during medical record chart review by a study provider. If treatment

was not provided on the same day as the visit, the date of treatment will be documented in the study database.

- b. Final analysis will present the treatment completion rate as the proportion of STIs where treatment was documented, by all STIs and by type.
 - c. Final analysis will present the time to treatment completion as the proportion of STIs treated same-day. Of the STIs not treated same-day, time to treatment will be presented as median number of days with an interquartile range.
6. Assess acceptability of pilot community-based care model
- a. Participants completed an acceptability survey following each study visit. Acceptability will be presented by study visit (i.e., enrollment, Month 3, and Month 6) as a proportion of all enrolled participants (N=50) who responded to the following questions:

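### Sustained use is met by one qualifying sample at Month 3 or Month 6 and reported as a single percentage, so it cannot show discontinuation between the two visits

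*Protocol*

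**What the plan says.** **PrEP (Protocol, Analysis Plan, item 3a).** Sustained use is tied to more than four doses a week, "resulting in a DBS TFV-DP concentration of >700 fmol/sample at 3 and/or 6 months post-enrollment among those prescribed PrEP at a preceding study visit". Item 3b reports it as one percentage.

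**MOUD (Analysis Plan, items 4a and 4b).** The timing is the same, "at 3 and/or 6 months post-enrollment among those prescribed MOUD at a preceding study visit", but the bar is lower: "Sustained use was defined as any buprenorphine and/or norbuprenorphine detected, resulting in a DBS >0 ng/mL concentration". The reporting line is "Final analysis will present sustained use for MOUD as a percentage (proportion"), with no split by visit.

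**Acceptability (Analysis Plan, items 6a and 7a).** These outcomes are explicitly broken down by enrollment, Month 3 and Month 6. Items 3 and 4 contain no such instruction.

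**Approach paragraph (opening summary).** It describes the assessment as "sustained use of PrEP and buprenorphine at months 3 and 6 (n=50"), which names both time points.

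**Background and rationale.** The problem is stated at six months: "sustained use of PrEP is exceedingly low (0-5%) among SHE Clinic patients after six months", with 12% for buprenorphine. The same section says that initial uptake at the existing clinic is high and that poor adherence and follow-through limit its impact.

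**Follow-up study visits.** Women not yet on PrEP or buprenorphine are offered them at Month 3 and Month 6, so some first prescriptions can fall at Month 3.

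**The concern.** Sustained use is a primary objective, and continuation is the gap that this pilot was set up to address. A rule satisfied by one sample at either visit does not measure continuation to six months. It records whether a woman qualified at least once, and it treats early use followed by stopping in the same way as use throughout.

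Two further features of the wording add to this. First, baseline starters have two opportunities to qualify over six months, while Month 3 starters have one, about three months after starting. Both enter the same percentage. Second, for MOUD the qualifying event is any detectable drug on one occasion, whereas for PrEP it is a level linked to a dosing frequency. The two percentages share a name but do not mean the same thing.

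The section Importance of Knowledge to be Gained says that a demonstrated benefit would support study at scale. A reader who sets the either-visit percentage beside the six-month background rates could take a difference in definition for an effect of the care model.

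**Working it through.** The protocol states no expected sustained-use rate and no sample-size calculation, so there is no planned figure to reproduce. The check is one of logic, followed by an illustration.

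**Step 1. Outcome patterns for a baseline starter.** Not positive includes having no sample.

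| Month 3 | Month 6 | Item 3a/4a, read literally | Use at Month 6 |
|---|---|---|---|
| positive | positive | sustained | yes |
| positive | not positive | sustained | no |
| not positive | positive | sustained | yes |
| not positive | not positive | not sustained | no |

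The second row is the difficulty.

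**Step 2. Size of the gap.** Let p3 and p6 be the proportions positive at Month 3 and Month 6 in the same women with the same denominator.

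- P(either) = p3 + p6 − P(both)
- P(either) − p6 = p3 − P(both) = P(positive at Month 3 and not positive at Month 6)

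This difference cannot be negative. It is zero only if nobody positive at Month 3 fails to be positive at Month 6.

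**Step 3. Illustration for MOUD.** Input from the protocol: p6 = 12% (Background and rationale). Assumptions: that this rate applies to women prescribed the drug; that p3 lies between 15% and 40%, since the protocol gives no Month 3 rate; and that all Month 6 users were also users at Month 3 (nested). Nesting gives the smallest gap for a given p3, and then P(either) = p3.

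| Assumed p3 | P(either), nested | Ratio to p6 |
|---|---|---|
| 15% | 15% | 0.15 / 0.12 = 1.25 |
| 20% | 20% | 0.20 / 0.12 = 1.67 |
| 30% | 30% | 0.30 / 0.12 = 2.5 |
| 40% | 40% | 0.40 / 0.12 = 3.3 |

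Without nesting the figure is higher. At p3 = 20%, independence gives 0.20 + 0.12 − 0.20 × 0.12 = 29.6%.

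**Step 4. Sensitivity to the denominator.** The background figures are given for clinic patients, and so is the buprenorphine uptake of 49%. If 12% is a share of all patients, six-month use among those who started would be 12 / 49 = 24.5%. A nested p3 of 25% then gives 0.25 / 0.245 = 1.02 times, and 40% gives 0.40 / 0.245 = 1.6 times. The ratio therefore depends on two quantities that the protocol does not supply.

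**Step 5. Pooling.** With nB baseline starters and nT Month 3 starters, the reported figure is (xB + xT) / (nB + nT), where xB counts women positive at either visit and xT counts women positive at Month 6. Adding the second group can move the percentage up or down. The inequality in Step 2 therefore holds for a fixed group and not automatically for the pooled figure.

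**The case against.** **The wording may mean visit-specific scoring.** And/or, followed by the condition on an earlier prescription, could describe two results: Month 3 among baseline starters, and Month 6 among baseline and Month 3 starters. The Approach paragraph fits that reading. But items 3b and 4b promise a single percentage, and the by-visit instruction in items 6a and 7a is absent here. At best the text is ambiguous on a primary objective, and the same remedy settles it.

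**No comparison is planned.** The Analysis Plan is purely descriptive, with no test against 0-5% or 12%. The protocol does not say how those rates were measured or on what denominator, so a Month 6 figure would not be strictly comparable with them either. This stands. It limits the harm to a misleading informal reading. It does not restore the missing information on discontinuation.

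**The size is assumed.** A reader might infer that the rule inflates sustained use several-fold. The documents do not support that: they give no Month 3 rates, and Step 4 shows that the ratio can be close to 1.

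**MOUD.** A reader might infer that one detection shows only recent exposure, and so ask for a current fill or a quantification limit in place of any level above zero. The protocol gives no detection window. Under Refill visits a woman "will be given a maximum of one month of therapy at a time", so a positive Month 3 sample in a baseline starter at least suggests use beyond the first fill. A fill requirement would create a new composite, and the assay cut-off can be left to the statistical analysis plan. What stands is that a single detection should be described as such.

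**Missing samples.** Counting every missing sample as failure would mix retention with drug use and would score women temporarily withdrawn under Incarcerated Participants as having stopped. It is reasonable as one end of a range, but not as the only rule.

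**The (n=50) in the Approach paragraph.** It may simply give the cohort size, so no contradiction with the Analysis Plan's denominator can be claimed.

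**Conclusion.** The point holds in a limited form. Read literally, items 3a and 4a count as sustained a woman who qualified at Month 3 and had stopped or been lost by Month 6, and they pool women with two chances and women with one. In fixed participants with a fixed denominator, the either-visit figure cannot be lower than the Month 6 figure. It exceeds it by the proportion positive at Month 3 and not positive at Month 6. That follows from the wording and needs no assumption about rates.

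How large the excess will be cannot be estimated from the protocol. The range of 1.25 to 3.3 times for MOUD illustrates assumed, nested Month 3 rates of 15% to 40% against 12% at Month 6. It is not a forecast.

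As reported, the percentage cannot show discontinuation between Months 3 and 6, and it should not be set against the six-month background figures. This is a small descriptive pilot with no hypothesis test, and drug-level samples are planned at both visits, so the information can be recovered by reporting it. It should be fixed, but it does not invalidate the study.

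**What to change.** - Report sustained use separately at Month 3 and at Month 6 for each drug, with Month 6 among women first prescribed at baseline as the headline.
- Show positive at both visits and positive at either visit as labelled extra rows.
- Show women first prescribed at Month 3 separately, as three-month persistence.
- At each visit give the number prescribed and the number with a sample. Present the result among those sampled and among all prescribed with missing counted as not sustained, and treat the two as a sensitivity range.
- Describe the MOUD measure as detection of buprenorphine or norbuprenorphine at the visit.
- State that the six-month background rates are context only, because their measurement and denominator are not given.
- Items 3a and 4a are written in the past tense, so the change may come after sample collection. Date it and show the result under the present definition alongside.

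**Cost.** Revised wording and a few table rows, with no additional samples or visits. The headline figure is likely to be lower, and the denominators will be smaller and the percentages less precise.

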Enrollment will occur at the time the informed consent document is electronically signed. Following enrollment, each participant will be given a unique study ID to prevent duplicate enrollments. The study ID will consist of the patient's last initial, first initial, and the day they were born. The baseline study visit will occur immediately following enrollment and will consist of completing a baseline health questionnaire, counseling for HIV risk reduction, counseling for treatment of opioid use disorder (if applicable), point of care (POC) STI testing, POC HIV testing, offering oral PrEP for HIV risk reduction (if applicable), and offering buprenorphine for treatment of opioid use disorder (if applicable). All participants will also be offered laboratory-based STI testing of the oral and rectal sites. Participants who consent for PrEP will also have phlebotomy performed for serum creatinine, hepatitis B serologies, and a 4th generation HIV antigen/antibody assay. Clinic staff will also address any immediate medical concerns of the participant and treat as able per standard of care. At the enrollment study visit, each participant will be given a \$25 Visa gift card for their participation.

In addition to reimbursement for each study visit, participants will receive a financial incentive of \$15 for returning to receive any test results that required off-site lab testing, as is standard of practice at our community partner, Aurora Commons/SHE Clinic. Participants on buprenorphine will also receive \$15 each time they return for monthly refills. Financial incentives will be paired with low-barrier, walk-in care and adherence counseling at each visit.

Baseline study visit data collection

An electronic health questionnaire will be filled out by participants in REDCap using a clinic tablet. Research staff will be allowed to assist the participant in filling out the electronic health questionnaire, if the participant chooses. The questionnaire will assess for risk factors for HIV, PrEP eligibility, prior use of PrEP, history of substance use, prior use of medications for opioid use disorder (MOUD), and current use of MOUD. At the end of the study visit, each participant will complete a brief electronic survey in REDCap. This survey will assess the patient's overall experience receiving care at the venue-based clinic and assess the level of acceptability and perceived stigma associated with venue-based care.

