	POC Trichomonas screening (self-collected vaginal swab)	X	X	X	
	POC CT/NG testing (self-collected vaginal swab)	X	X	X	
	Hair sample collection (for TFV and Bupe levels)	X	X	X	
	Dried Blood Spot (for TFV and Bupe levels)	X	X	X	
	Financial Incentive for Returning for Results (following study visits)	X ^b	X ^b	X ^b	X ^b
^a only for those who consent to billing/insurance claim					
^b If clinically indicated					

Lab Processing and Results Delivery

Study specific labs will include hair sample and DBS collection for detection of tenofovir and buprenorphine levels, as well as self-collected vaginal swabs for POC STI testing and POC fingerstick HIV and syphilis testing.

Hair testing:

Hair samples will be sent to the Hair Analytical Laboratory (HAL) at the University of California San Francisco (UCSF-HAL). The HAL uses liquid chromatography-tandem mass spectrometry (LC-MS/MS) for testing. The HAL has found high rates of acceptability and feasibility (>95%) of collecting hair samples among U.S. adolescents and women. Our group has experience with hair collection across studies and has found it acceptable.

HAL will test hair sample for tenofovir and buprenorphine levels, as indicated based on medications prescribed to each participant. Results of hair sample testing will be used for research purposes only to determine adherence to prescribed medications, and results will not be returned to the individual participant.

DBS testing:

Dried blood spots will be obtained at baseline and at quarterly follow-up visits (Month 3 and Month 6) using a lancet finger stick to express drops of blood onto a 5-spot DBS card. This will be done following collection of a blood droplets from finger for the HIV/syphilis rapid test. The card will be labeled with participant ID and transported to PI's locked office where they will be securely stored for possible TFV and buprenorphine testing.

POC STI testing:

Chlamydia and Gonorrhea testing

Participants will give their self-collected vaginal swab specimen to clinic staff prior to survey completion. Participants will collect a vaginal swab in a private space in the study clinic. POC STI tests for *C. trachomatis* and *N. gonorrhoeae* will be available within 30 minutes using a small, FDA approved, CLIA waived PCR machine supplied by Binx Health. POC STI samples

will be processed in real time, with results delivered to participants during the study visit, and no samples stored.

Trichomoniasis testing

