Research Material Obtained from Participants

Individuals who are eligible and enroll in venue-based care will complete a baseline, 3-month and 6-month study visit. Data to be collected at those visits include information on demographics, risk factors for HIV, PrEP eligibility, prior use of PrEP, history of substance use, prior use of medications for opioid use disorder (MOUD), current use of MOUD, and self-reported adherence to PrEP and/or MOUD, as indicated. Participants will also provide information on their experience accessing venue-based care, including acceptability and perceived stigma associated with accessing venue-based care. POC HIV testing, POC STI testing, and standard of care labs for PrEP will be obtained at baseline, 3-months and 6-months. Hair samples and DBS samples to test for tenofovir and buprenorphine will be obtained at 3-month and 6-month visits. A review of the participants medical and pharmacy records will be conducted.

Assessment data will be collected directly onto iPads used by research team members. We will utilize the Research Electronic Data Capture (REDCap) system through the University of Washington's Institute of Translational Health Services (ITHS) to log and store data.

Women who are started on buprenorphine therapy will also return for monthly refill visits, during which time no additional study data will be collected.

Risks to Human Subjects

There are limited physical risks to study subjects beyond what is incurred during standard primary care. Participants may experience mild bruising or pain at the site of point of care finger prick testing (e.g., POC HIV and syphilis testing, DBS sampling), or at the site of phlebotomy draws. Participants who choose to initiate on oral PrEP and/or buprenorphine will be at risk of experiencing established side effects, as outlined in each drugs' prescribing materials.

Participants may experience psychological distress associated with discussing confidential topics such as sexual and drug use practices. Research medical team staff will be trained in trauma-informed care and to address psychological distress with a calm, non-judgmental attitude. We will take steps to minimize any psychological discomfort by ensuring confidentiality as described below. We will only enroll patients who understand the study procedures and are willing to participate.

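### Sustained MOUD use (Analysis Plan, item 4a) pools women the clinic started with women already on buprenorphine who accepted a study prescription, so it describes use but cannot show the clinic's impact unless split by drug status at first prescription

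*Protocol*

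**What the plan says.** Item 4a of the Analysis Plan sets the numerator: "Sustained use was defined as any buprenorphine and/or norbuprenorphine detected, resulting in a DBS >0 ng/mL concentration". It sets timing and denominator as "at 3 and/or 6 months post-enrollment among those prescribed MOUD at a preceding study visit". Neither part refers to drug status at entry. Item 3a (PrEP) also has no baseline term, but it uses a concentration cut-off: "Sustained use was defined as >4 doses/week, resulting in a DBS TFV-DP concentration of >700 fmol/sample at 3 and/or 6 months post-enrollment".

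Other sections bear on this:

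- **Eligibility.** The inclusion and exclusion criteria do not mention current buprenorphine or PrEP use.
- **Prescribing.** Under Data Collection Overview, the offer of buprenorphine follows active self-reported opioid use and interest. Not being on buprenorphine already is not a condition. Women not yet started can also be offered it at follow-up visits.
- **Baseline questionnaire.** It records "prior use of medications for opioid use disorder (MOUD), and current use of MOUD".
- **Baseline DBS.** The DBS testing section says "Dried blood spots will be obtained at baseline and at quarterly follow-up visits (Month 3 and Month 6", Table 1 marks DBS at month 0, and item 4a says "DBS samples were obtained at each visit to assess MOUD adherence via buprenorphine and norbuprenorphine concentrations". The section on research material obtained from participants differs: "Hair samples and DBS samples to test for tenofovir and buprenorphine will be obtained at 3-month and 6-month visits".
- **Purpose.** The General Overview, Data Collection Overview and Involvement of Human Subjects sections all present uptake and sustained use as measures of the clinic's impact.
- **History.** Background and rationale gives six-month sustained use at the SHE Clinic as 12% for buprenorphine and 0-5% for PrEP, with buprenorphine uptake of 49%.

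**The concern.** With a threshold of any detection, a woman taking buprenorphine on the day she enrols already meets the numerator criterion. If she accepts a study prescription and is still positive at Month 3 or Month 6, she counts as sustained use although nothing has changed since entry. A woman who was off buprenorphine, was started by the clinic and stayed on it counts the same way. The single percentage cannot tell the two apart.

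What is at stake is interpretation. There is no control arm, and the SHE Clinic figures are the only sustained-use rates from this setting that the protocol offers for context. The protocol also says that a demonstrated benefit would support study at larger scale. A percentage raised by women who arrived already on treatment could be taken for such a benefit.

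**Working it through.** The protocol states no sample-size derivation, target rate or test for this outcome, so there is no figure to reproduce. The check has two parts.

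**1. Who can enter the numerator**

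- On outside buprenorphine, no study prescription: not in the denominator, so not counted.
- On buprenorphine at entry, accepts a study prescription, positive later: counted. No eligibility, prescribing or scoring rule removes her.
- Not on buprenorphine at entry, accepts a prescription, positive later: counted.

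Item 2a measures uptake by acceptance of a prescription, and item 4a requires only that MOUD was prescribed. A positive sample therefore need not come from the study supply.

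**2. How far pooling could move the percentage (illustration)**

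Inputs:

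- *b*, share of prescribed women already positive: **not in the documents**; 12% to 40% assumed.
- *r*, share of those still positive at follow-up: **not in the documents**; 50%, 70% and 90% assumed.
- 12%: the SHE Clinic figure, assumed to apply to women not on drug at entry, as a stand-in for no clinic effect.
- Number prescribed: 50 × 0.49 = 24.5, taken as 24 or 25. This assumes that SHE Clinic uptake carries over.

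Reported rate = *b* × *r* + (1 − *b*) × 0.12. The excess over 12% is *b* × (*r* − 0.12).

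Example with *b* = 20%, *r* = 70%: 0.20 × 0.70 + 0.80 × 0.12 = 0.140 + 0.096 = 23.6%.

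| *b* | *r* = 50% | *r* = 70% | *r* = 90% |
|---|---|---|---|
| 12% | 16.6% | 19.0% | 21.4% |
| 20% | 19.6% | 23.6% | 27.6% |
| 30% | 23.4% | 29.4% | 35.4% |
| 40% | 27.2% | 35.2% | 43.2% |

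The excess vanishes as *b* goes to 0 or *r* falls to 12%.

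Suppose someone compared the result with 12%, which the protocol does not plan. The exact 95% lower limit first exceeds 12% at 7 positives (12.6% for 7/24, 12.1% for 7/25). The binomial chance of 7 or more, for 24 and 25 women, is:

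- *b* = 0: 1.9% and 2.4%
- *b* = 12%, *r* = 70%: 15.4% and 18.1%
- *b* = 20%, *r* = 70%: 33.1% and 37.4%
- *b* = 30%, *r* = 70%: 58.6% and 63.5%

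Among women negative before their first prescription, the rate in this illustration is 12% whatever *b* is.

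**PrEP.** Starting from 5%, with *b* of 5% to 10% and *r* of 50% to 90% (assumed):

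- lowest: 0.05 × 0.50 + 0.95 × 0.05 = 7.3%
- highest: 0.10 × 0.90 + 0.90 × 0.05 = 13.5%

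**The case against.** A reader might infer that item 4a credits the clinic with any buprenorphine use that predates it, and that the reported rate will be inflated by a calculable amount. The documents do not support that reading.

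- **The prescription requirement is a real, though partial, safeguard.** It removes women on outside buprenorphine who take no study prescription. The overlap that remains is possible under the rules, but nothing shows that it is common.
- **The current-use question is weak evidence of buprenorphine at entry.** MOUD is broader than buprenorphine, and a methadone clinic is among the recruitment sites.
- **The plan is descriptive.** Item 4b reports a percentage. No test against 12% and no success threshold are stated. Keeping a woman on treatment is sustained use, so the percentage is correct for what it describes.
- **Any single-arm proportion can be above zero without a clinic effect.** This remains true after a split, because a woman negative at entry can obtain buprenorphine elsewhere.
- **The numbers rest on assumed shares.** The SHE Clinic's 12% and 49% are not the share already positive among women prescribed here. The Background also says buprenorphine adherence and retention may be below 50% at six months, so the higher values of *r* may be generous.
- **PrEP is a weaker case**, given the cut-off above 700 fmol and the low historical use.

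All of this stands, and it limits the point to interpretation. It does not remove the point. The protocol itself fixes the scoring rule, the rule pools two different groups, and the protocol wants the result to speak to impact. A separate SAP could add a split without contradicting item 4a, but as written the rule gives one pooled figure.

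**Conclusion.** The point holds in limited form. Item 4a validly describes buprenorphine use among women the study prescribed for. It does not support a statement about the clinic's impact, or a comparison with the SHE Clinic's 12%, because it mixes women started by the clinic with women continuing.

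The size is unknown. Under the assumed values the reported rate would be 16.6% to 43.2% where women not on drug at entry have 12%. These figures show sensitivity and are not an estimate of bias. They depend on *b* and *r*, which the documents do not give, and on using 12% for the remaining women. The protocol also does not say how the 12% was measured or whether it pools in the same way. For PrEP the structure is the same and the likely effect small.

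**What to change.** 1. Keep the overall percentage in item 4a as the description of use among prescribed women.
2. Also report it separately for (a) women with no buprenorphine or norbuprenorphine in the DBS taken at or before the visit of first study prescription (enrolment or Month 3) and (b) women with drug detected then. Base any statement on the clinic's impact on group (a). Using the visit of first prescription matters because a woman negative at enrolment may be positive from another source by Month 3, when she is first prescribed.
3. If that DBS is missing, classify by buprenorphine-specific EMR or pharmacy records and by self-reported current buprenorphine use. The general MOUD item should not be used alone, since it may include methadone.
4. Reconcile the statement that DBS is taken at Months 3 and 6 only with the DBS testing section, Table 1 and item 4a, which include baseline. The follow-up visit section asks for DBS only from women who received a prescription, so state that a woman first prescribed at Month 3 gives a sample at that visit.
5. The same split can be reported for PrEP in item 3a, as a lower priority.

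**Cost.** Analysis-plan wording, and assay of pre-prescription cards for prescribed women only; most of these cards are already scheduled. The clinic-started group is smaller and its percentage less precise. For example, if 5 of 25 women were positive beforehand, the standard error at 12% would rise from √(0.12 × 0.88 / 25) = 6.5 points to √(0.12 × 0.88 / 20) = 7.3 points. Group (b) may also include women who moved from non-prescribed to prescribed buprenorphine, which may be a real clinic effect. Both groups should therefore be shown.
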